### 11. PROCEDURES INVOLVED\*

After informed consent has been obtained, subjects will be randomized to receive either of the study medications medication: 250mg of acetazolamide or a placebo pill. Investigator will be blinded as to which arm of the study the patient is enrolled. Medications will be obtained from the UMass Pharmacy in individual blister packs. We will ensure that acetazolamide and the chosen placebo pill look similar. Any identifying information on the blister pack will be obscured by a black marking pen, if necessary. Medications will then be inserted into small opaque envelopes and marked with only a number. Numbers will be assigned to medications by use of the random number generator function (=RANDBETWEEN(1,30\*)) (\*The final number will depend on the total number of subjects) in Excel with the top half of the list being assigned Acetazolamide and the bottom half placebo pill. The list will then be sorted in numerical order in Excel. When a subject enrolls, a number will be assigned in order. Blinding of the numbers and assigned medications as well as the assembly of the envelopes will be done prior to leaving UMass by PI's faculty advisor who will not be involved in medication administration.

At each of the time points noted in #9, lung ultrasound exams will be done at bedside in a private location to measure the total ultrasound lung comets (an ultrasound finding for pulmonary edema) for a "comet score." One (1) single dose of 250mg acetazolamide or placebo will be given at Everest Base Camp (Data Collection #4) and a comet score will be measured again 12 hours after acetazolamide or placebo is given. Previous studies have shown that comet scores increase with altitude and given that Everest Base Camp is the highest altitude the subjects will be residing at, it is believed that we will find the biggest decrease in comet score if acetazolamide is given at this point. The subject's heart rate and oxygen saturation will also be collected via a pulse oximeter.

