#### **13. Data Analysis and Management\***

Previous studies in lung ultrasonography suggest that a minimum of 14 subjects will be needed to provide 80% power to detect a statistically significant difference in ultrasound lung comets. Between 20-30 total subjects are expected.

For data analysis, Fisher's exact test will be used to compare categorical variables. Continuous variables will be analyzed with paired Student's t-test. Linear regression models will be used to assess correlations between ultrasound lung comets and vital signs. In all cases p values < 0.05 will be considered significant. Data will be reported as mean +/- SD

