**19. MULTI-SITE RESEARCH\***

This study is being conducted simultaneously with study #H00014129. While the studies are on the same subjects, the studies are expected to minimally impact each other. The main potential effect the studies could have on each other is the time that will take for each to be completed at a time point, however neither data collection is expected to take more than 20 minutes per subject. The pulmonary ultrasound measurements of study #H00014860 are short duration and not expected to impact cognitive function or the ability of subjects to answer questions on the concussion software. The concussion apps in this study do not require physical exertion except minimal effort during a short time standing and balancing and are not expected to impact pulmonary edema or the ultrasound measurements.

Study #H00014860 involves a single dose of acetazolamide or placebo at Everest Base Camp. The concussion app data for this time point will be collected before the medication is given and therefore should not be impacted. An additional data point 12 hours later at Everest Base Camp will be added to assess any effect of the medication on the concussion app data for study #H00014129. While this study's main goal is not to assess the effect of acetazolamide on the cognitive functions measured by the concussion apps, it may add useful information both for this study and for study #H00014860. The half-life of immediate release acetazolamide is 5-6 hours and is expected to have been excreted prior to the next time point six days later after descent.

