**26. CONFIDENTIALITY**

Data will be collected including patient's vital signs and will be recorded with ultrasound images and data collection sheet. This information will be obtained from the study subject via pulse oximetry. The medical record will not be accessed. Digital images of ultrasound exams will be recorded for later review as described. Ultrasound images are recorded and stored on the password-protected encrypted handheld Android tablets during the duration of the trek. These images will be transferred to a secure password-protected hard drive in the locked offices of the Division of Emergency Ultrasound once back in the United States. Access to these images will be limited to study personnel and the UMASS IRB.

No patient identifiers (e.g. name, medical record number) will be linked to this information. A unique subject ID will be used to track data and link to ultrasound images. Final results of image interpretation by expert reviewer will be stored in an Excel spreadsheet in the UMass servers.

Only study personnel and the UMASS IRB will have access to the data. All study paperwork including electronic database information will be maintained for 3 years following completion of the study.

In the case that subjects are suspected of having HAPE during the trek, subject's information may be shared with trek leaders. Subject information may be subjected to different or fewer confidentiality protections than exist under US regulations, because the research is being conducted internationally. It is possible, although unlikely, that information may be shared with trek leaders, other medical personnel, or otherwise subject to subpoena in cases of severe illness/injury or death.

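### The comet and vital-sign regression does not say how up to six sessions per subject are handled; both obvious readings can push false positives well above 5%

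*Combined protocol and SAP*

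**What the plan says.** Section 13 (Data Analysis and Management) gives this analysis one sentence, "Linear regression models will be used to assess correlations between ultrasound lung comets and vital signs", followed by the general rule "In all cases p values < 0.05 will be considered significant". It does not say which sessions enter, and it names no subject effect, session or altitude term, or clustered standard error. The sentence before it names a paired t-test, so pairing within subject is recognised there but not carried over to the regression.

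The data are repeated measures. Section 11 (Procedures Involved) says "At each of the time points noted in #9, lung ultrasound exams will be done at bedside", and the section 9 itinerary lists six: Data Collection (DC) 1 to 6. Section 11 adds that "heart rate and oxygen saturation will also be collected via a pulse oximeter", without repeating that this happens every time. Section 26 (Confidentiality) describes "vital signs and will be recorded with ultrasound images and data collection sheet", so paired readings at each session are likely.

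Two further facts matter. Section 11 says "Previous studies have shown that comet scores increase with altitude". It also says "a comet score will be measured again 12 hours after acetazolamide or placebo is given", so DC5 and DC6 follow dosing. The attached grant proposal is cited for background and scanning method, not for the analysis.

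**The concern.** Ordinary linear regression treats every row as independent. With 20-30 subjects and six sessions, a pooled analysis has 20 × 6 = 120 to 30 × 6 = 180 rows but still only 20-30 independent people. If a subject with high comets tends to stay high, and a subject with low saturation tends to stay low, chance alignment between people is counted up to six times over. The standard error is then too small.

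Running one regression per session avoids that problem but gives six chances of p < 0.05 for each vital sign.

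The target is also unclear. Comets rise with altitude. If a vital sign also changes with altitude (an assumption), a pooled slope mixes two questions: whether the two move together up the mountain, and whether subjects with worse vital signs have more comets at a given altitude.

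At stake is whether a link reported as significant between comets and heart rate or saturation can be believed. Section 13 does not label this analysis exploratory.

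**Working it through.** **Inputs.** From the documents: 20-30 subjects (section 13); m = 6 sessions on March 28, April 1, 4, 7, 7 and 13 (section 9), with DC5 placed 12 hours after dosing (section 11), giving days 0, 4, 7, 10, 10.5 and 16; alpha 0.05, taken as two-sided because the plan does not say. Assumed: the ICCs and the correlation decay. The plan has no error rate of its own for this regression to reproduce. Its minimum of 14 subjects for 80% power concerns the comet difference.

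**Reading 1: sessions pooled, equal correlation between sessions.** With no true link, the slope variance is understated by

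D = 1 + (m − 1) × ICC(comets) × ICC(vital sign),

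and the true error rate is 2 × [1 − Φ(1.96/√D)].

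| ICC in both | D | Formula | Simulated, N = 20 / 30 |
|---|---|---|---|
| 0 | 1 | 5.0% | 5.1% / 5.2% |
| 0.3 | 1 + 5 × 0.09 = 1.45 | 10.4% | 9.6% / 10.3% |
| 0.5 | 1 + 5 × 0.25 = 2.25 | 19.1% | 18.6% / 18.6% |
| 0.7 | 1 + 5 × 0.49 = 3.45 | 29.1% | 29.1% / 29.1% |

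The product of the two ICCs drives the result. With 0.3 and 0.7, D = 1 + 5 × 0.21 = 2.05 and the error is 17.1%. If either ICC is zero, D = 1 and the error is 5%.

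**Reading 1 with decaying correlation.** Let the correlation between two sessions be ρ = ICC + (1 − ICC) × exp(−days apart/τ) in both variables. Then D = (1/6) × the sum of ρ² over all 36 ordered pairs of sessions (each session with itself included). The formula gives:

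| τ (days) | ICC 0 | ICC 0.3 | ICC 0.5 |
|---|---|---|---|
| 2 | 8.0% | 14.7% | 22.5% |
| 4 | 12.1% | 19.7% | 26.3% |
| 8 | 20.0% | 26.6% | 31.3% |

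Simulation agrees, so the range over this grid is about 8-32%.

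**Reading 2: one regression per session, unadjusted.** For six independent tests, 1 − 0.95^6 = 26.5%. Correlation between sessions lowers this: to about 21-22% at an equal ICC of 0.7, and about 19% with τ = 8 and ICC 0.5. Across all runs the range is about 19-28% per vital sign; values slightly above 26.5% are simulation spread.

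**Reading 3: a single session chosen in advance.** Simulated error at DC4 is 4.5-5.4%.

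**Altitude trend.** Suppose each variable shifts by 0.5 SD between 3440 m and 5364 m, with no link at a given altitude. Pooled regression then rejects in 26% / 36% of trials (N = 20 / 30) at ICC 0 and 33% / 41% at ICC 0.5.

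**Checking remedies.** Session and arm terms with ordinary standard errors leave 9.4-28.8% at ICC 0.3-0.7. Subject fixed effects with ordinary standard errors leave 7.2-11.8% when correlation decays. Session and arm terms with leave-one-subject-out jackknife standard errors and t on N − 1 degrees of freedom gave about 4-6% throughout, including cells with 20% early withdrawal, skewed comets or an altitude trend.

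**The case against.** The strongest objection is that the plan never says rows are pooled. The plural in section 13 fits separate models per session at least as well, and section 11 does not itself say vital signs are taken every time. This stands: a reader might infer that the plan commits to a pooled analysis with up to 29% false positives, and the documents do not support that. But the separate-models reading carries its own 19-28% chance of a false positive, so the silence does not make the analysis safe.

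The ICCs are also assumed. At 0.1 in both variables the pooled error is only 5-6%. That stands, which is why a range is shown.

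A reader might take 29% as a ceiling. It is not: decaying correlation reaches about 32%, and a shared altitude trend gives higher rejection rates. Those last rejections should not all be called false positives, because they partly reflect a real across-altitude correlation.

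The choice of target belongs to the investigators. Rising comets with altitude are part of the study's rationale, so the across-altitude relation may be what they want. That is fair, and the fix leaves it open.

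An arm term at DC6 may look unnecessary, since section 19 expects the drug to be gone before "the next time point six days later after descent". The case for the term is clearest at DC5; at DC6 it is a precaution.

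**Conclusion.** The gap is real and minor. Section 13 applies a p < 0.05 rule to a regression on repeated measurements without saying which sessions enter or how subjects are accounted for. Of the natural readings, only one pre-chosen session holds about 5%.

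The pooled figures (about 10-29% with equal correlation, about 8-32% with decay) need clustering by subject in both variables, at levels the documents do not give. The per-session figure of about 19-28% needs no assumed clustering, only six unadjusted tests. Mixing of across-altitude and same-altitude relations depends on a vital sign changing with altitude, which is also assumed.

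A reader might infer that the treatment result is in doubt. It is not: this regression is neither the primary nor the secondary outcome in the study endpoints (section 10), and the acetazolamide comparison does not depend on it.

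**What to change.** Replace the regression sentence in section 13 with text such as:

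> Comet score will be regressed on heart rate and, separately, on oxygen saturation in one model each using all available sessions, with session (DC1-DC6) as a factor, a treatment-arm term after dosing, and standard errors clustered by subject with a small-sample correction (leave-one-subject-out jackknife, t with number of subjects minus 1 degrees of freedom). Slopes and 95% CIs will be reported as exploratory.

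If the investigators want the within-subject or the across-altitude association instead, they should say so before analysis and keep the subject-clustered standard errors. Adding subject fixed effects gave 4.3-5.3% error in the cells tried, or a conservative 3.2-3.7% with skewed comets.

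**Cost.** A few sentences, no new data and standard software. The interval is wider than the pooled one. At ICC 0 the mean widths are 0.408 against 0.364 for N = 20 (12% wider) and 0.319 against 0.296 for N = 30 (8% wider). At ICC 0.7 they are 0.754 against 0.365 and 0.588 against 0.296, about double. Above ICC 0 this is mostly because the pooled interval is too narrow. The new interval is still 24-59% narrower than one from DC4 alone (for N = 20, 0.754 against 0.992 at ICC 0.7 and 0.408 against 0.988 at ICC 0).

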**9. STUDY TIMELINES\***

**H00014860 Acetazolamide on High-Altitude Pulmonary Edema**  
**Version 2 – 02/10/2018**  
**INVESTIGATOR STUDY PLAN**

We will recruit subjects from the 2018 Wilderness Medical Society (WMS) Everest Base Camp Trek. The WMS 2018 Everest Base Camp Trek is a trekking trip from Lukla, Nepal (2840m) to Everest Base Camp (5400m) in Spring 2018. The duration of the trek is approximately 3 weeks. The duration of enrollment will be approximately 1-2 days during preparation part of the trip in Kathmandu, Nepal at the beginning of the trek. The estimated date for completion of primary analyses will be December 2018.

WMS Everest Base Camp Trek Itinerary

March 25	Arrival in Kathmandu, transfer to hotel (1310m)
March 26	Sightseeing in Kathmandu and preparation day **Enrollment day**
March 27	Fly to Lukla (2840m), trek to Phakding (2610m)
March 28	Trek to Namche (3440m) **Data Collection 1**
March 29	Namche and slow walk to Kunde Hospital/Kumjung
March 30	Extra day in Namche and visit Namche Bazar (3440m)
March 31	Trek to Tengboche (3860m)
April 1	Trek to Pheriche (4270m) **Data Collection 2**
April 2	Pheriche / hike Nakarsang Hill (5200m)
April 3	Pheriche
April 4	Lobuche (4910m) **Data Collection 3**
April 5	Gorakshep (5140m)
April 6	Hike to Kalapathar (5550m) / Everest Base Camp (5364m)
April 7	Everest Base Camp (5364m) **Data Collection 4 & 5**
April 8	Pheriche
April 9	Khumjung (3760m)
April 10	Manjo (2835m)
April 11	Lukla(2840m)
April 12	Fly back to Kathmandu
April 13	Kathmandu farewell dinner **Data Collection 6**
April 14	Final departure to home

\* May change slightly depending on weather, conditions, etc.

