**10. STUDY ENDPOINTS\***

Primary outcome measures: 1.) Pulmonary edema detected in lung ultrasound exams before and after taking acetazolamide.

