## INVESTIGATOR STUDY PLAN

Secondary outcome measures: 2.) Time to completion of ultrasound exams

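### Section 13 calls every p<0.05 significant without naming the comparisons or one confirmatory test, and its only test for continuous data does not compare the randomised arms

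*Combined protocol and SAP*

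**What the plan says.** Section 13 (Data Analysis and Management) assigns Fisher's exact test to categorical data and linear regression to the relation between lung comets and vital signs. For the rest it says "Continuous variables will be analyzed with paired Student's t-test". It closes the testing rules with "In all cases p values < 0.05 will be considered significant". It contains no list of comparisons, order of testing, multiplicity adjustment or named confirmatory test.

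Section 9 schedules six sessions. The dose is given at Everest Base Camp, where the itinerary places "Data Collection 4 & 5". The last session, "Data Collection 6", follows the return to Kathmandu. Section 11 confirms the schedule: "At each of the time points noted in #9, lung ultrasound exams will be done at bedside". It also adds two vital signs: "The subject's heart rate and oxygen saturation will also be collected via a pulse oximeter".

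Section 10 gives one primary outcome, "Pulmonary edema detected in lung ultrasound exams before and after taking acetazolamide", and one secondary outcome, "Time to completion of ultrasound exams". Section 11 places the post-dose scan 12 hours after the dose and says that earlier studies found comet score to rise with altitude.

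**The concern.** The significance rule covers every test that section 13 allows, and section 13 does not limit how many there are. With six sessions and a two-session test, any use of Data Collections 1, 2, 3 or 6 means choosing pairs, and nothing stops that choice being made after the data are seen.

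The randomised comparison is also left without a test. A paired t-test of session 4 against session 5 measures change over 12 hours at Base Camp. Pooled over arms, it mixes drug and placebo. Within the acetazolamide arm alone, it cannot separate the drug from acclimatisation or time. Fisher's exact test could compare arms, but only if edema were made a yes/no variable, and the plan gives no comet-score cut-off for that.

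In a study of 20-30 subjects, a chance change between two sessions in saturation or heart rate could therefore be reported as significant on the same terms as the drug effect.

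**Working it through.** **The plan's own figure.** The plan states no overall error rate. Its one related number is a minimum of 14 subjects for 80% power (section 13). This cannot be reproduced, because no effect size, SD or test is given. Solving backwards at two-sided 0.05 and 80% power, 14 subjects correspond to a standardised effect of 0.81 for a paired test, or 1.63 for two arms of 7. The power statement therefore does not show which comparison was meant.

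**Inputs from the documents.** Six sessions (section 9). Comet score, heart rate and oxygen saturation (section 11). Exam time (section 10). Threshold 0.05 with no adjustment (section 13). Expected size 20-30 subjects, minimum 14 (section 13).

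**Assumptions.** Two-sided tests, normal data, no true difference between any sessions, and a stated correlation between sessions. The number of comparisons is also an assumption, because the plan does not give it.

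**Step 1: possible comparisons per variable.** One (session 4 vs 5); five (consecutive sessions, or each session against the first); or all pairs, 6 x 5 / 2 = 15.

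**Step 2: independence as a reference.** The chance of at least one p<0.05 in k independent tests is 1 - 0.95^k. This gives 5% for k = 1, 22.6% for k = 5 and 53.7% for k = 15. Tests that share sessions are not independent, so the 15-pair case needs simulation.

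**Step 3: simulation.** Paired t-tests on six correlated sessions, n = 14, 20, 25 and 30, with 20,000 datasets per setting. Correlation was either equal between all sessions (0, 0.5, 0.8) or decaying with distance (first-order autoregressive, 0.5 and 0.8).

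| Comparisons run on one variable | Chance of at least one p<0.05 |
|---|---|
| Session 4 vs 5 only | about 5% |
| Each session vs the first (5) | 15-19% |
| Consecutive sessions (5) | 20-23% |
| All 15 pairs, decaying correlation | 33.5-36.8% |
| All 15 pairs, equal correlation | 37.6-39.4% |

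As a cross-check, the studentised range for six means at the unadjusted critical value gives 35.5-36.6%. It pools the variance, whereas the simulation estimates it separately for each pair, so a slightly lower figure is expected.

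**Step 4: one session pair, several variables.** A single 4-vs-5 test on each of four variables gives 1 - 0.95^4 = 1 - 0.8145 = 18.5%, if the variables were independent. Section 13 plans to relate comets to vital signs, so independence is only a convenience here.

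**Step 5: the altitude question.** Data Collections 1-4 are at 3440, 4270, 4910 and 5364 m, with mean 4496 m. The squared deviations sum to 1,115,136 + 51,076 + 171,396 + 753,424 = 2,091,032. With equal correlation, in units of the within-subject variance, the estimated total rise from a linear trend has variance 1924^2 / 2,091,032 = 1.77. A single paired test of session 1 against 4 has variance 2.00. The trend is modestly more precise, and it replaces several tests by one.

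**The case against.** The strongest reply is that the plan already has a hierarchy. Section 10 names a single primary outcome and labels exam time secondary, and sections 9 and 11 place the before and after scans at Data Collections 4 and 5. If that is the only confirmatory comparison, its error rate is 5%. This stands, and it is why the range must start at 5%. It does not close the point, because section 10 names an outcome and not a test. It leaves open whether edema is a score or a yes/no finding, and whether the arms are pooled, taken separately or compared.

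A reader might infer that the plan carries a 38% false-positive risk per variable, or that it commits to 15 x 4 = 60 tests with a 76-85% chance of a false finding across three or four variables. The documents do not support either reading. They never say that all session pairs will be tested. Heart rate and saturation are not listed as outcomes, and their one specifically named analysis is regression against comets. The 76-85% figures also treat related variables as independent. For comet score, the plan itself expects a rise with altitude, so many of the 15 differences would be real and could not be false positives.

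A reader might also infer that paired tests are a weak way to show the altitude effect. Against a single test of session 1 versus 4, variances of 1.77 and 2.00 do not bear that out. The trend model is a supporting suggestion only.

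**Conclusion.** The concern holds as a gap in specification combined with an unrestricted significance rule. Section 13 declares every p<0.05 significant, does not name the comparisons, and gives the randomised contrast in comet score no test. The resulting risk is not one number. Per variable it is about 5% for sessions 4 vs 5 only, about 15-23% for five contrasts, and about 34-39% for all 15 pairs. These rates assume that no session truly differs, that tests are two-sided, and that sessions are correlated as in the simulation. The top of the range is near a worst case for comet score. Testing sessions 4 vs 5 on four variables would give about 19% under independence. The point is worth correcting before analysis, but it does not show that the primary comparison, once properly defined, would have an inflated error rate.

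**What to change.** Replace the significance sentence in section 13 with a statement on these lines:

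- p<0.05 is claimed for one confirmatory test only: the acetazolamide-placebo comparison of the change in comet score from Data Collection 4 to Data Collection 5.
- Exam time, heart rate, oxygen saturation, other session comparisons and the regressions are secondary or exploratory, and are reported as estimates with 95% confidence intervals.
- If the rise with altitude is tested, it is one trend of comet score on altitude over Data Collections 1-4, in a mixed model with a random intercept per subject, labelled secondary, in place of several paired tests.

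This changes wording only and adds no subjects, sessions or measurements. The downside is that fewer results may be called significant. The 14-subject power statement should then be tied to the named comparison, because it does not say which test it refers to.

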Acetazolamide is a drug that has been approved by FDA for use of prevention of acute mountain sickness. Acetazolamide is not approved for prevention of HAPE and is investigational for this study. While it is FDA-approved to be used to treat acute mountain sickness, many previous studies and current guidelines have recommended the use of acetazolamide prevention HAPE. The investigation does not involve a route or dosage level that significantly increases the risks associated with the use of the drug product. This investigation does not involve a patient population that would significantly increase the risks associated with the use of the study drug.

Bedside ultrasound is a non-invasive modality of imaging that is routinely used and employed in clinical practice. It does not involve input of radiation into the subjects or an invasion of the subject's privacy. Subjects thoraces will be scanned in a private setting in lodging. Both left and right thoraces will be scanned. 28 total ultrasound images will be recorded during each session (16 on the right and 12 on the left). Please see attached WMS grant proposal page 2-5 for details of the methods of ultrasound scanning. Each session is expected to take approximately 5 minutes.

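### Section 13 gives the comet score, a zero-bounded count, no comparison between arms and no stated scale: a paired t-test does not test acetazolamide against placebo, and mean and SD may describe skewed counts poorly

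*Combined protocol and SAP*

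**What the plan says.** Section 11 (Procedures Involved) has the investigator "measure the total ultrasound lung comets" at each session, over 28 images (16 right, 12 left). One dose of acetazolamide or placebo is given at Everest Base Camp at Data Collection 4, and the score is taken again 12 hours later (Data Collection 5 in section 9). The reason given for that timing is that "Previous studies have shown that comet scores increase with altitude" and that "it is believed that we will find the biggest decrease in comet score if acetazolamide is given at this point".

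Section 10 words the primary outcome as "Pulmonary edema detected in lung ultrasound exams before and after taking acetazolamide", without naming a metric or scale.

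Section 13 (Data Analysis and Management) assigns Fisher's exact test to categorical variables. For the rest, "Continuous variables will be analyzed with paired Student's t-test" and "Data will be reported as mean +/- SD". It mentions no transformation, count model, rank test, median or distribution check, and no comparison of acetazolamide with placebo on a continuous outcome. It says that 14 subjects give 80% power and that 20-30 are expected.

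**The concern.** Two gaps sit in the same lines of section 13.

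The first concerns the comparison. Subjects are randomised to drug or placebo, but the only test offered for a continuous outcome is within-subject. A significant fall in the acetazolamide arm could reflect 12 more hours at the same altitude, repeat scanning or regression to the mean. The placebo arm is there to remove those explanations, and a paired test does not use it for that.

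The second concerns the scale. A total of comets is bounded at zero and may be right-skewed. With 10-15 subjects per arm, a few high scorers can then dominate the variance of raw change and hide a real fall, and mean and SD summarise such data poorly. If the scale is left open, it may be chosen after 20-30 values have been seen.

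**Working it through.** **The plan's own figure.** The 14 subjects cannot be reproduced, because section 13 gives no effect size, SD or sidedness. It can only be solved backwards at two-sided 5% and 80% power (1.96 + 0.84 = 2.80):

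- All 14 as pairs: standardised change 2.80/√14 = 0.75 (0.81 with the t distribution).
- Seven per arm: standardised difference 2.80 × √(2/7) = 1.50 (1.63 with the t distribution).

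The figure can be neither confirmed nor refuted, and it does not show which test was meant.

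**What the paired test estimates.** Let τ be the mean 12-hour change without drug and δ the drug's added effect. The paired test tests τ + δ = 0 in the acetazolamide arm, τ = 0 in the placebo arm, and τ + δ/2 = 0 if equal arms are pooled. Only the difference between arms isolates δ.

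**Effect of scale on power.** All inputs here are assumed: lognormal subject means with median 10, session noise of log-SD 0.35, Poisson counts, comets halved on acetazolamide and unchanged on placebo, two-sided 5%, 4000 simulated trials per setting. Power in %:

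| Subjects | Between-subject log-SD | Raw change, arms compared | Raw ANCOVA | Log ANCOVA | Added by adjustment | Added by log scale |
|---|---|---|---|---|---|---|
| 30 | 0.6 | 51 | 75 | 78 | 24 | 3 |
| 30 | 0.9 | 44 | 62 | 72 | 18 | 10 |
| 30 | 1.2 | 34 | 51 | 68 | 17 | 17 |
| 20 | 0.9 | 30 | 43 | 52 | 13 | 9 |

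The log scale is log(1 + comets). Under no effect, the log analysis rejected in 4.4-6.2% of trials.

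**Sensitivity to the assumed median.** Raw ANCOVA to log ANCOVA:

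- Log-SD 0.6, median 5: 42% to 44% (20 subjects), 63% to 62% (30 subjects).
- Log-SD 0.6, median 3: 34% to 35% (20), 49% to 51% (30).
- Log-SD 0.9, 30 subjects: 53% to 58% (median 5), 46% to 48% (median 3).

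Over medians 3-20 and log-SDs 0.3-1.2, the change runs from about -3 to +20 points.

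**A second model** (mean 15, 10 per arm, halving, visit noise of log-SD 0.3) agrees in direction. For between-subject CV 0.5, 1.0 and 1.5, raw to log:

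- ANCOVA: 68% to 71%, 53% to 61%, 40% to 48%.
- Paired test within the acetazolamide arm: 80% to 83%, 64% to 76%, 50% to 69%.

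At mean 5 and CV 0.5 the paired test gains nothing (56% and 56%), and with 15 per arm it loses 2 points (77% to 75%).

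**If the fall is additive.** With symmetric scores of mean 20 and a fall of 5, raw against log ANCOVA is 76% against 72% (20 subjects) and 91% against 89% (30), a loss of 4 and 2 points. With skewed scores and an additive fall floored at zero (mean 15, CV 1, fall 5, 10 per arm), the log scale is still better for the paired test: 78% to 92%.

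**Mean minus SD.** This is negative only when the SD exceeds the mean. With mean 15, an SD of 7.5 gives +7.5, 15 gives 0 and 22.5 gives -7.5. At median 10 in the first model it is negative in about 10% of trials at log-SD 0.6 and 50-60% at 0.9. Computed within one arm at log-SD 0.9, the share is 39-49%.

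**What log(1 + comets) estimates.** A halving from 10 to 5 reads (1+5)/(1+10) = 0.55, from 5 to 2.5 it reads 3.5/6 = 0.58, and from 3 to 1.5 it reads 2.5/4 = 0.63. The simulated averages are close to these (about 0.54 at median 10 and 0.62 at median 3).

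**The case against.** The strongest reply is that the scale argument rests on a distribution the documents never describe. That stands: with low counts or little skew the log scale gains nothing and can cost a point or two. Most of the apparent gain over a raw change score at log-SD 0.6-0.9 also comes from baseline adjustment (24 of 27 points in the first row of the table).

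Four stronger readings are tempting, and the documents or the method do not support them.

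- A reader might infer that section 11 specifies a proportional effect. It compares altitudes and gives no ratio; a larger absolute fall because there is more room to fall fits as well.
- A reader might infer that section 13 states that raw totals will be tested. That is the natural reading, but the text is silent on the variable and the scale, and section 10's wording could even be taken as categorical.
- A t-test on differences does not assume that everyone falls by the same amount. It tests the mean difference, and skewed differences cost efficiency.
- The SDs are not error bars on the mean. They describe spread, and the plan does not call them error bars.

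It is also fair to say that a log(1 + comets) contrast is not a ratio of comets, so the remedy has to label its estimate correctly. None of this answers the missing comparison between arms.

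**Conclusion.** The point holds in a limited form. On the text alone, the outcome is a zero-bounded count, section 13 does not name its scale, and the only test for continuous variables does not compare the randomised arms. The missing comparison is the larger defect, and changing the scale would not repair it.

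The loss from an untransformed analysis is conditional on skew. For an assumed halving of comets with 20-30 subjects, log-scale over raw-scale ANCOVA is worth about -3 to +20 points of power, and about 7-10 points at median 10 and log-SD 0.9. Baseline adjustment itself is worth about 13-24 points over a raw change score at median 10 and log-SD 0.6-0.9. A negative mean minus SD is likewise a possibility that depends on skew. No median, SD or effect size used here comes from the documents.

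**What to change.** In section 13:

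- Name the total comet score as the primary variable. Make the primary analysis a comparison of acetazolamide with placebo at Data Collection 5, adjusted for the score at Data Collection 4.
- Fix the scale before unblinding. Either use log(1 + comets) for both scores and label the back-transformed effect a ratio of (1 + comets), or use a count model that allows for overdispersion and gives a ratio of comets. Report the effect with its 95% CI.
- Keep the baseline-adjusted difference on the raw scale as a supporting analysis.
- Describe the comet score at each session by median and interquartile range.

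The cost is wording only; no visit or procedure changes. The downsides are that the effect reads as a ratio, that log(1 + comets) understates the comet reduction when counts are low (a true 0.50 reads about 0.62 at median 3), and that about 2-4 points of power are lost if the effect is additive on symmetric scores.
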